Online Platform for Healthy Weight Loss (POEmoS)

February 9th, 2018

STUDY PROTOCOL

Design

This is a three-arm parallel randomized controlled trial which recruited adults (18-60 years) participants classified as overweight or obese (body mass index – BMI ≥ 25 kg/m²) and who had the intention to lose weight.

Participants and recruitment

Students (current and past) and staff of the Federal University of Minas Gerais (UFMG), Belo Horizonte, in the southern Brazil, were recruited by physical and online advertising (flyers, University website, UFMG mailing list) for one month from the 25th September to 24th October, 2017. They were invited to access the project website www.poemasufmg.com.br, where they can watch a video with details of the project. Interested participants can join the project online and create an account profile after checking for the inclusion and exclusion criteria (Table 1) and signing the informed consent form. Participants excluded from the study can reference colleagues by entering their email.

Table 1- Inclusion and exclusion criteria for recruitment into “POEmas (Online Platform for healthy weight loss)” Randomized Clinical Trial

Inclusion criteria	Exclusion criteria
Age between 18 and 60 years	Pregnancy
BMI* ≥ 25 kg/m ²	Self-report of comorbidities that demand specific dietary or physical activity recommendations- diabetes, heart failure, coronary artery disease, kidney disease, hepatic disease, cancer, phenylketonuria, celiac disease, food allergies, bariatric surgery history
Intention to lose weight by changes in	Participation in any other weight loss

lifestyle habits	program
Internet access	

* BMI: Body mass index

Randomization and allocation

Once informed consent was obtained, participants were randomly allocated to one of the three groups using a stratified randomized block design. Participants were stratified by gender and category of body mass index (25 to <30 or ≥ 30 kg/m²) using blocks of variable length (either 3 or 6).

Participants were initially allocated to one of three groups:

- (1) Group 1, control group which is submitted to an initial minimal intervention for 24 weeks and subsequently will have access to all the platform functionalities;
- (2) Group 2 will follow a standard weight loss program delivered by the website platform for 24 weeks;
- (3) Group 3 followed the standard weight loss program enhanced by personalized feedback by a nutritionist based on lifestyle habits reported in the platform for 12 weeks and the standard weight loss program for the following 12 weeks.

Subsequently, subjects received an automatic email with detailed information on the groups they were allocated to. Researchers were blinded to participants' allocation.

Outcome measures

All outcomes will be assessed at baseline, 12 and 24 weeks afterwards. Weight and BMI change are the primary outcomes of the study and will be self-reported by the participants. Secondary outcomes will be changes in dietary habits, food-related behaviors, physical activity habits, sedentary behaviors, quality of life, health perception, online activity and users' satisfaction, as detailed in Table 2. Outcome assessors will be blinded to group allocation.

Sample size

Based on a 90% power to detect a significant difference of 4kg weight loss between groups, assuming the SD of weight is 6.0 and using a two-sided significance level of 0.05, and a 40% attrition rate, a sample size of 90 participants was calculated for each group.

Interventions

The interventions will be delivered online for 24 weeks, with new program content distributed to the user weekly for Groups 2 and 3. The content of dietary and physical activity recommendations was based on Brazilian and international evidence-based guidelines. Dietary recommendations focused on particular Brazilian habits. Physical activity recommendations focused on increasing time of leisure exercise and decreasing sitting time.

In group 1, subjects have access to four videos with information on health consequences of excessive weight, dietary and physical activity weight loss recommendations, as well as strategies to behavior change. They also received an e-book with lifestyle habits and behavioral recommendations to lose weight. Access to the study website will be limited for the first 24 weeks and they have been asked not to undertake any other weight-loss program during this time. They will be invited to report their weight, dietary and physical activity habits at 12 and 24 weeks after baseline by email. Afterwards, they will gain access to the standard online platform.

Group 2 has access to the study website program for 24 weeks. The platform used in this study was adapted from a commercial product (Cybergia® Inc.), which runs various Internet-based health programs in Brazil (www.cybergia.com). The platform is cloud-based progressive, web-app developed and can be accessed in desktop and smartphone environments. It has three areas: 1) Main area, presenting weekly updated tasks such as content (video, articles), suggested dietary and physical activities and questionnaires; 2) Self-monitoring area, containing a food diary, functionalities for activity self-report and charts; 3) Social area, containing a private social network where users can share and react to photos and posts. Connecting these areas, the platform presents gamification mechanics, such as weekly points (connected to completing tasks and interacting with other participants) and social challenges, which invite users to complete one-time

specific tasks and share their accomplishments. Interaction with the project's team was restricted to public posts and selected comments on the social network.

Group 3 has access to this online program plus weekly individual chat in the platform with a dietitian. At these times, they have the opportunity to discuss and manage individual issues.

Quality Control

Several procedures will be employed to optimize the quality of the study and maximize internal validity and reliability of the program delivery and outcome assessments. Assessors of the main outcome measures are blinded to the participants' group allocation. Assessment protocols and orientations to participants were standardized in written documents. Validation of self-reported weight and height will be performed by correlation to measurements for a random sample of 10% of the study population. Personnel will be trained on anthropometry procedures prior to the assessment. Regular team meetings between the clinical and information technology teams, in order to align strategies, are planned.

Measurements and instruments

Demographic Data

Data on gender, education, civil status and place of work will be collected at baseline. Questionnaires to obtain current medical conditions and medications will be completed at baseline and 24 weeks.

Anthropometry

Weight and height will be self-reported by the participants and BMI will be calculated by the formula weight in kg/ (height*height) in m². For the random 10% sample selected for additional measurements, weight will be measured in light clothing, without shoes on a Welmy ® analogic scale with stadiometer. For this sample, waist circumference will be measured at the mid-level between the last rib and the iliac crest using an inelastic tape and body composition will be measured by electrical bioimpedance using Sanny ® Bioimpedance.

Dietary intake and food-related behavior

For groups 2 and 3, calculation of the total daily caloric intake and dietary nutrients will be performed by an automatic dietary calculator which was based on food nutrition composition tables for the Brazilian population (<http://www.unicamp.br/nepa/taco/>).

Questions about the total number of daily serves of fruit and vegetables, and whole carbohydrates sources, as well as weekly serves of sweetened beverages and snack foods will be applied. Moreover, food-related behaviors, including number of days taking breakfast, number of daily meals, frequency of take-away food consumption and eating while watching television will be assessed by questionnaires.

Eating behavior

The random sample selected to anthropometry will have cognitive and behavioral components of eating assessed across three scales of cognitive restraint, uncontrolled eating and emotional eating by the Brazilian version of the Three Factor Eating Questionnaire-R21, (TFEQ-R21).

Physical activity and sedentary behavior

- The short-form of the International Physical Activity Questionnaire (IPAQ) will be used to estimate total MET-minutes/week and to classify participants into either high, medium or low physical activity categories according to the IPAQ Scoring Protocol [18].
- The daily screen-time (i.e., in front of TV, computers, video games, smartphones) and the daily sitting time will be used to assess sedentary behavior.
- Pedometers: the number of steps will be measured by XXX pedometer in the sample randomly selected to anthropometry.

Health perception

The Brazilian version of the *12-item Short-Form Health Survey – Version 2*, (QualityMetric Incorporated, Lincoln, RI, USA) which is a self-reported measure of health-related quality of life (HRQoL) designed to investigate multidimensional aspects

of physical and mental health for the general population and those with chronic diseases, will be applied to all participants.

Self-rated health will be assessed by one question derived from the Short-Form-36(SF-36)- "In general, you say your health is..." with "excellent", "very good", "good", "regular" or "bad" as alternative answers.

Body image perception and satisfaction will be assessed by a scale in which the participant can choose his current and ideal silhouette from 15 options, according to gender.

Online activity and satisfaction with the weight loss program

Self-monitoring entries, posts and comments in forums and chats will be collected and stored in the platform database and exported as CSV files. For Group 3, we also analyzed the number of interactions with the nutrition specialist. To assess users' satisfaction with the weight loss program and with the web-based platform we will develop and apply a specific questionnaire.

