Online Platform for Healthy Weight Loss (POEmaS)

February 9th, 2018

DATA ANALYSIS PLAN

Analysis will be on an intention-to-treat basis. Outcomes will be analyzed at two timepoints (12 and 24 weeks). Analysis of covariance will be used to test for differences in weight loss between groups at each time point. The models will be fitted using linear regression with weight as the outcome variable, treatment group as the predictor variable of interest and weight at baseline included as a covariate. Age, gender, dietary intake (kilocalories) and physical activity at baseline will enter the model for adjustment. Statistical significance of the primary efficacy analysis (at 12 and 24 weeks) will be based on Hochberg's multiple testing procedure with the family wise error rate for each time point held at 2.5%. Secondary hypothesis tests will be performed using a 2-sided 5% significance level.

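### BMI category is a randomisation stratum but is missing from the primary model, at a small cost in precision if it predicts follow-up weight

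*Protocol*

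**What the plan says.** The protocol, under Randomization and allocation, states: "Participants were stratified by gender and category of body mass index". The two categories are 25 to <30 and ≥30 kg/m². Within the four resulting strata, allocation to the three arms was made "using blocks of variable length (either 3 or 6").

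The SAP describes a linear regression with "weight as the outcome variable, treatment group as the predictor variable of interest and weight at baseline included as a covariate". It then adds: "Age, gender, dietary intake (kilocalories) and physical activity at baseline will enter the model for adjustment". This model is used at 12 and at 24 weeks.

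Gender is therefore in both the allocation and the analysis. BMI category is in the allocation only. Neither BMI in any form nor height is listed as a covariate, no reason is given, and no sensitivity analysis includes the category.

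**The concern.** A factor used to stratify allocation is normally carried into the primary model. Stratifying balances the factor across arms, but it does not take the factor's contribution out of the residual; only modelling it does that. If BMI category predicts follow-up weight given the covariates already listed, the residual variance is larger than it need be and the intervals for the arm contrasts at both time points are slightly too wide. Balance at randomisation is also not guaranteed among those who remain after the 40% attrition the protocol allows for.

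The choice is unexplained as well. Three variables that played no part in allocation (age, energy intake, activity) are in the model, and one of the two variables that did is not. What is at stake is precision and consistency between design and analysis, not validity.

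**Working it through.** **1. The plan's own sample size.** Inputs from the protocol's Sample size section: 90% power, a target difference of 4 kg, and 90 per group. The other inputs read "assuming the SD of weight is 6.0 and using a two-sided significance level of 0.05, and a 40% attrition rate".

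- n per group = 2(1.960 + 1.282)² × 6² / 4² = 47.3, so 48 completers. Dividing by 0.6 gives 80.
- The stated 90 is not reproduced, but it is on the safe side at 5%: 90 × 0.6 = 54 completers per arm.
- SE of an arm contrast = 6 × √(2/54) = 1.155 kg. By the normal approximation, power for 4 kg is 93.4% at two-sided 5% and 88.9% at two-sided 2.5%.

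The mismatch over 90 is a separate matter. The present point does not depend on it.

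**2. How much of the category the model already carries.** The documents give no population figures, so these are assumed: 75% or 50% women; height 1.62 m (SD 0.065) in women and 1.75 m (SD 0.07) in men; BMI = 25 + gamma(shape 1.6, scale 3.2), which puts 41% at ≥30 kg/m². Regressing the category on baseline weight and gender gives R² of about 0.43 for either sex mix. The rest is left over because BMI depends on height, which the model lacks.

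**3. Approximate cost of omission.** Let b be the category's effect on follow-up weight given the other covariates.

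- Leftover variance of the category: 0.41 × 0.59 × (1 − 0.43) ≈ 0.137.
- SE ratio, without / with, before any cost of the extra term: √(1 + 0.137 b² / 36).
- b = 1 kg: 1.002. b = 2 kg: 1.008. b = 4 kg: 1.030.
- Estimating the extra term costs about √(154/153) = 1.003, taking 162 completers and 8 parameters in the planned model.
- Net cost of omission: about nil at 1 kg, 0.5% at 2 kg and 2.7% at 4 kg.

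**4. Simulation.** 8,000 trials per setting: 270 randomised in stratified blocks of 3 or 6, 40% random dropout, residual SD 6 after the category, true difference 4 kg. The model contained arm, baseline weight, age and gender, with or without the category. Energy intake and activity were not simulated.

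| Category effect | SE without / with, 75% women | SE without / with, 50% women | Change from omission |
|---|---|---|---|
| 0 kg | 1.164 / 1.167 | 1.166 / 1.168 | 0.2–0.3% smaller |
| 1 kg | 1.167 / 1.167 | 1.168 / 1.168 | none |
| 2 kg | 1.173 / 1.167 | 1.175 / 1.168 | 0.5–0.6% larger |
| 4 kg | 1.200 / 1.167 | 1.201 / 1.168 | 2.8% larger |

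A separate simulation, with 70% women and with noise terms for energy intake and activity in the model, gave SEs without / with of 1.183 / 1.177 at 2 kg and 1.208 / 1.176 at 4 kg: 0.5% and 2.7%.

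**5. Power for a single contrast at two-sided 2.5%.** The answer depends on what the protocol's SD of 6.0 stands for.

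- If 6.0 is the residual after the category, simulated power is 86.9% with it. Without it, power is 86.4–86.6% at 2 kg and 84.8–85.4% at 4 kg, a loss of about 0.3–0.5 and 1.5–2 points.
- If 6.0 is the residual under the planned model, power is 88.9% as in step 1. Adding the category gives an SE of 1.155 × 1.167/1.173 = 1.149 and power of 89.3% at 2 kg. At 4 kg the SE is 1.155 × 1.167/1.200 = 1.123 and power is 90.7%.

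**6. Type I error without the category.** At nominal 2.5% with 75% women: 2.2% (2 kg) and 2.0% (4 kg), Monte Carlo error 0.17 points. In the separate simulation at nominal 5%: 4.6% to 5.5%. There is no inflation, and the estimates showed no material bias.

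**The case against.** The strongest reply is that the harm rests on an effect the documents do not give. At 0 kg the planned model is marginally better, and at 1 kg there is nothing between the two. If weight change is proportional to baseline weight, baseline weight absorbs it and the conditional category effect is zero. If change varies by 0.2 kg per BMI unit, the conditional effect is about 0.6 kg and adding the term is a slight net loss. At 0.5 kg per unit it is about 1.5 kg, costing about 0.4% before the degree of freedom is paid for. On this linear form a 4 kg effect needs about 1.3 kg per unit. The mean BMI gap between categories in the assumed population is about 6.4 units, so that implies roughly 8.4 kg between the categories in weight change, against a design difference of 4 kg. Energy intake and activity, which are in the planned model, might absorb a little more.

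This stands as to size: the 2.8% and the 1.5–2 power points belong to an extreme case.

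The absolute power levels are also loosely anchored. The protocol's claim is 90% at 5%, and 2.5% is only the most lenient Hochberg step. With three contrasts the strictest is 2.5%/3 = 0.83%, where the step 1 formula gives 79.6%. The comparison with and without the category matters more than the level.

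None of this removes the omission. Baseline weight without height is not BMI, and the balance of risks favours inclusion: at most about 0.3% lost if the category is irrelevant, and up to 2.8% recovered over the range examined.

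**Conclusion.** The point holds, and it is minor. The primary model leaves out one of the two stratification factors without a reason. The test stays valid. The likely cost lies between nothing and about 0.6% in the standard error for conditional effects up to 2 kg; 2.8% at 4 kg is an outer bound. The omission itself is plain from the two documents. Whether precision is actually lost depends on a category effect they do not supply, and the figures rest on the assumed population, random dropout and a residual SD of 6.0.

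**What to change.** Add BMI category as recorded at randomisation (25 to <30, ≥30 kg/m²) as a term in the primary model at 12 and 24 weeks, alongside gender and baseline weight. The protocol also says "Weight and BMI change are the primary outcomes of the study", whereas the SAP writes out a model for weight only; the model for BMI change should carry the same term.

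If the sponsor prefers to omit the category, the SAP should say why, though a reason alone recovers no precision.

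The cost is one term in the model statement and one degree of freedom. The variable already exists because it was needed to randomise. If it proves not to be prognostic, the standard error rises by about 0.2–0.3%.

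### The stated inputs give 80 to 82 per group, not 90, and the 6.0 is labelled an SD of weight where an SD of weight change (or residual SD) is needed

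*Protocol*

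**What the plan says.** The Sample size section of the protocol sets a power of 90% for a 4 kg difference in weight loss between groups. The remaining inputs appear there as "assuming the SD of weight is 6.0 and using a two-sided significance level of 0.05, and a 40% attrition rate". The result reported is that "a sample size of 90 participants was calculated for each group". The section names no test, does not say which of the three possible comparisons was sized, gives no source for the 6.0, and mentions no rounding or safety margin.

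The Outcome measures section makes change in weight and in BMI primary. Under Randomization and allocation, "Participants were stratified by gender and category of body mass index", with the cut at 30 kg/m²; eligibility starts at a BMI of 25 and has no upper limit.

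The SAP compares groups at 12 and 24 weeks by analysis of covariance on weight, with "weight at baseline included as a covariate" and further baseline adjusters. Its primary tests use Hochberg's procedure with a family-wise rate of 2.5% at each time point. The number of comparisons in the family is not given, nor is the sidedness of that 2.5%.

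**The concern.** A sample size paragraph should let a reader get from the inputs to the number. This one does not, and the input that drives the result carries the wrong name. For a difference in weight loss analysed with baseline weight in the model, the noise that matters is the SD of each person's change, or the SD left in follow-up weight once baseline is known. The spread of body weight between people is a different and much larger quantity.

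What is at stake is interpretation. If a comparison at 12 or 24 weeks is not significant, readers will ask whether 4 kg was detectable. The stated 90% is not what the inputs give at 0.05, nor what they give at the level the SAP will use. And the 6.0 cannot be checked against the trial's data until it is clear which SD it is.

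**Working it through.** **Inputs.** From the protocol's Sample size section: difference Δ = 4 kg, SD σ = 6.0 (taken as kg), two-sided α = 0.05, power 90%, attrition 40%, 90 per group. From the SAP: family-wise 2.5% per time point. Equal allocation follows from equal group sizes and blocks of 3 or 6.

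**1. The plan's own figure.** For two means, n = 2(z₁₋α/₂ + z₁₋β)² σ²/Δ².
- n = 2 × (1.960 + 1.282)² × 36/16 = 47.3, so 48 analysed per group. The t-test version gives 49.
- Enrolled: 48/0.6 = 80; 49/0.6 = 81.7, so 82.
- The stated 90 is 8 to 10 higher.

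**2. Can 90 be reached another way?**
- Inflating by 1.4 instead of dividing by 0.6: 68 to 69.
- Three-group ANOVA at 0.05: 97 for means 0, 2, 4; 74 for means 0, 4, 4.
- Allowance for a rank test (efficiency 0.955): 85 to 87.
- Two-sided 0.025: 94 to 97.
- One-sided 0.05/3: 89 to 90. This matches, but contradicts the stated two-sided 0.05.
- Changing one input: 90 would need attrition of 1 − 49/90 = 45.6% to 1 − 48/90 = 46.7%, or an SD of about 6.35 (t) to 6.41 (normal) in place of 6.0.

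Of the variants tried, none that keeps the stated two-sided 0.05 gives 90.

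**3. Power that 90 per group gives.** Analysed: 90 × 0.6 = 54. The standard error of the difference is 6 × √(2/54) = 1.155, and 4/1.155 = 3.464. Normal power is Φ(3.464 − z₁₋α/₂).

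| Two-sided level | z | Normal | t-test |
|---|---|---|---|
| 0.05 | 1.960 | 93.4% | 93.0% |
| 0.025 | 2.241 | 88.9% | 88.1% |
| 0.025/3 | 2.638 | 79.6% | 77.9% |

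Under Hochberg, a comparison can be significant only if its p-value is at most 0.025, and always is if its p-value is at most 0.025/m. With m = 3 pairwise comparisons (an assumption), the power for any one comparison with a true 4 kg difference therefore lies between the last two rows. The 2.5% is read as two-sided, because the protocol sizes two-sided and two time points at 2.5% sum to 5%.

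**4. What 6.0 can be the SD of.** The documents give no SD data, so this step rests on assumptions.
- As an SD of body weight: take heights of 1.62 m (SD 0.06) in women and 1.75 m (SD 0.07) in men, with 50% to 80% women. With everyone at exactly BMI 25, the SD of weight is already 6.8 to 7.8 kg. With BMI of mean 30 and SD 3 to 5, it is about 12 to 17 kg.
- As a residual SD given baseline, σ√(1 − ρ²): with SD of weight 15 kg and ρ = 0.85, 0.90 or 0.95, it is 7.9, 6.5 or 4.7 kg. With 12 kg and ρ = 0.90 or 0.95, it is 5.2 or 3.7 kg.
- As an SD of change, σ√(2(1 − ρ)): with 15 kg at both times and ρ = 0.92, it is 15 × √0.16 = 6.0 kg.

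So 6.0 kg falls inside the plausible range for a residual SD or an SD of change, and below any plausible SD of body weight under these assumptions.

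**The case against.** The sentence that gives the SD also says that the difference sized is in weight loss, and the primary outcome is change. In that context 6.0 reads naturally as the SD of weight change, and the slip is one missing word. That stands: the value need not change, only its label.

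The gap between 80 to 82 and 90 is small and favours the trial. Rounding or an unstated margin could explain it. That also stands at two-sided 0.05, although the protocol mentions neither. It does not carry over to the SAP's level: a single two-sided test at 0.025 needs 94 to 97 enrolled, so 90 falls slightly short of 90% power there.

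Recruitment ran to 24 October 2017 and both documents are dated 9 February 2018. Replacing 90 by a target of 80 to 82 would therefore do nothing. That stands too, and the fix leaves the target alone.

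A reader might infer more: that 6.0 kg is an impossible input, and that with a realistic spread of body weight the trial is badly underpowered. The documents do not support this. It would apply to an unadjusted comparison of raw follow-up weights, which neither document plans; the SAP puts baseline weight in the model. Nor does the surplus of 8 to 10 show that some other analysis was sized. The clear departures from the SAP are the significance level and the absence of any mention of baseline adjustment.

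**Conclusion.** The point holds as two correctable faults in one paragraph. First, the stated size and power do not correspond: the inputs give 80 to 82 enrolled per group for 90% power, and 90 enrolled gives 93% for one test at two-sided 0.05. On its own inputs the trial is not undersized. Second, the SD is attached to the wrong quantity. It is a mislabelled input, plausible as an SD of weight change or a residual SD, with no source given.

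At the SAP's per-time-point level the power is about 88% for one two-sided test. It falls to about 78% for a comparison that has to pass at 0.025/3. The arithmetic in steps 1 to 3 uses the protocol's own inputs, takes attrition as exactly 40%, and ignores the few degrees of freedom spent on covariates. The 88% assumes that the 2.5% is two-sided; a one-sided 2.5% would return the single-test figure to 93%. The 78% also assumes three pairwise comparisons. The plausibility check on the SD rests on assumed heights, BMI spread and correlations.

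**What to change.** Make two changes in the protocol's Sample size section, and leave enrolment as it is.

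1. Relabel the input: *assuming an SD of weight change (or residual SD of follow-up weight given baseline weight) of 6.0 kg*. Say which of the two is meant and give its source.
2. Restate the power of the chosen size: *90 per group, 54 analysed after 40% attrition, gives about 93% power for one two-sided test at 0.05 and about 88% at two-sided 0.025, the SAP's family-wise level at each time point*. Add that power is lower, down to about 78%, for a comparison that has to be significant at 0.025/3 if the Hochberg family has three pairwise comparisons.

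The SAP should state the number of comparisons in the family and the sidedness of the 2.5%, so that the last two figures can be confirmed or replaced.

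The cost is a few sentences. No participants, visits or data are added.

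### The 90% power claim belongs to a single test at two-sided 0.05, not to the SAP's Hochberg test at 2.5% per visit; whether power falls short depends on choices the documents leave open

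*Protocol*

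**What the plan says.** The Protocol, under Sample size, gives the basis as "Based on a 90% power to detect a significant difference of 4kg weight loss between groups, assuming the SD of weight is 6.0", and continues "using a two-sided significance level of 0.05, and a 40% attrition rate, a sample size of 90 participants was calculated for each group". It does not say which pair of groups or which visit is meant, and it makes no allowance for multiple testing.

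The SAP, under Data Analysis Plan, bears the same date. It fits a linear regression with "treatment group as the predictor variable of interest and weight at baseline included as a covariate" and further baseline covariates. It bases primary significance at 12 and 24 weeks on Hochberg's "multiple testing procedure with the family wise error rate for each time point held at 2.5" per cent. It does not list the contrasts in the family or give the sidedness of the 2.5%. Sidedness appears only in the next sentence: "Secondary hypothesis tests will be performed using a 2-sided 5% significance level". On the analysis set and the visits it says "Analysis will be on an intention-to-treat basis. Outcomes will be analyzed at two timepoints (12 and 24 weeks"), with no method for missing data.

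Under Outcome measures, the Protocol names two primary outcomes: "Weight and BMI change are the primary outcomes of the study and will be self-reported by the participants". The SAP does not say whether BMI change is in the Hochberg family.

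**The concern.** The sample size and the primary test use different significance levels, and neither document connects them. If the 2.5% is two-sided, no contrast at either visit can be declared significant with p above 0.025, so nothing is tested at the 0.05 used for sizing. With three arms there are at least two contrasts, and Hochberg can push the threshold for a given contrast lower still.

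What is at stake is how a non-significant contrast is read. It would be taken to come from a trial with a 10% chance of missing a true 4 kg difference. For one named contrast at one visit, before any covariate gain, that chance is about 13–21% if the 2.5% is two-sided and 8–14% if one-sided. Type I error is not affected.

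**Working it through.** **Inputs.** From the Protocol's Sample size: difference 4 kg, SD 6.0, power 90%, two-sided 0.05, attrition 40%, 90 per group, hence 90 × 0.6 = 54 analysed. From the SAP: Hochberg at 2.5% per visit. Three equal arms, from Randomization and allocation. Assumed here: no covariate gain, and only the 54 are analysed.

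**1. The plan's own figure.** n per group = 2 × SD² × (z₁₋α/₂ + z₀.₉)² / Δ².
- At 0.05: 2 × 36 × (1.960 + 1.282)² / 16 = 47.3, so 48. The exact t calculation gives 48.3, so 49.
- Inflated for attrition: 48 / 0.6 = 80; 49 / 0.6 = 81.7, so 82.

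The stated inputs therefore need 80–82 per group, not 90. The figure does not reproduce; the difference is in the conservative direction.

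**2. Power of a single test with 54 per group.** Standardised difference = 4 / (6 × √(2/54)) = 3.464.
- At 0.05: Φ(3.464 − 1.960) = 93.4%; exact t 93.0%.
- At two-sided 0.025: Φ(3.464 − 2.241) = 88.9%; exact t 88.1%.

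So about 88% is the ceiling for any one contrast at one visit if the 2.5% is two-sided. At that level 90% power needs 57.1, so 58 completers (exact t), against 54. The surplus from step 1 does not close the gap.

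**3. Hochberg at 2.5%, one visit.** With two contrasts, both are significant if the larger p is at most 0.025; otherwise the smaller must be at most 0.0125. With three, the successive thresholds are 0.025, 0.0125 and 0.00833. Simulation (at least 400,000 replicates, 54 per arm, SD 6.0, one pooled variance) gives:

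| Family | True loss in groups 1/2/3 (kg) | Group 3 v 1, two-sided | Group 3 v 1, one-sided | At least one true 4 kg contrast, two-sided |
|---|---|---|---|---|
| Two v control | 0/4/4 | 87.1% | 92.3% | 93.3% |
| Two v control | 0/0/4 | 82.6% | 88.8% | 82.6% |
| Two v control | 0/2/4 | 83.0% | 89.0% | 83.0% |
| Three pairwise | 0/0/4 or 0/4/4 | 81.5% | 87.9% | 90.4% |
| Three pairwise | 0/2/4 | 79.1% | 85.7% | 79.1% |

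One-sided 2.5% was run as two-sided 5%. Strictly directional p-values change that column by less than half a point (second row 88.4%).

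**4. What moves these figures** (two-sided; every assumption in this step is external to the documents).
- Covariates: if 6.0 is a raw SD, an R² of about 8–23% restores 90% for a named contrast. If it is a change or residual SD, the gain may be small or already counted.
- Visits: a named contrast detected at either visit has power of about 84–95%, and at both visits about 67–83%, for between-visit correlations of 0.5–0.9.
- BMI in the family (equal standardised effect, correlation with weight 0.90–0.99): 77–85% with four tests, 73–76% with six.
- Losses: 97–99% if all 90 give data with the full effect; 77–85% if the lost 40% are entered as zero change.

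**The case against.** The strongest reply has four parts.

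First, 2.5% at each of two visits sums to the 5% in the Protocol, so the levels can be squared. That holds for total type I error. It does not hold for power, because the sizing gives the whole 0.05 to one test and the SAP gives it to none, if the 2.5% is two-sided. A one-sided 2.5% is numerically a two-sided 5%; under that reading only the Hochberg step differs, and the power range straddles 90%.

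Second, the Protocol names no pair of groups. If success means finding at least one true 4 kg difference, 90% is met at a single visit with a two-sided test and no covariate gain, provided the family contains two such contrasts. This stands, and it makes any shortfall depend on the success definition. It does not rescue the claim when only one contrast is 4 kg (79–83%).

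Third, the SAP's analysis is covariate-adjusted and by intention to treat, so unadjusted completers are not its test either. This also stands as a limit on the figures. But the Protocol claims no covariate gain, itself assumes 40% attrition, and describes 6.0 only as the SD of weight, while the SAP names no method for the missing values.

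Fourth, the excess of 90 over 80–82 is conservative. True, but 54 completers already include it.

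A reader might infer that the trial is underpowered for its primary analysis. The documents do not support that: several admissible readings reach or exceed 90%. They support only that the stated 90% was derived for a different test.

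**Conclusion.** The mismatch is real and should be fixed. The 90% refers to one comparison at two-sided 0.05; the SAP applies Hochberg at 2.5% per visit to an unlisted family. For a named 4 kg contrast at one visit, the two-sided reading lies about 3 to 11 points below 90%, and the one-sided reading runs from about 4 points below to 2 above.

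These figures rest on 54 analysed per group, SD 6.0 and no covariate gain. The direction and size of any departure from 90% depend on seven things the documents do not settle: the contrasts, the sidedness, whether success means a named contrast or at least one, the visit, the type of SD, whether BMI is in the family, and how losses are handled. Confidence is high in the mismatch and in the arithmetic discrepancy; a loss of power is possible but not shown.

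**What to change.** Keep the record of how 90 per group was chosen and correct its arithmetic: at two-sided 0.05 the stated inputs need 80–82 per group, and 90 gives 93%.

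Then add a statement of power under the SAP's test. It should name the contrast family, the sidedness of the 2.5%, the success definition (a named contrast or at least one), the visit, and whether BMI is in the family. It should also say that 54 analysed per group is assumed, how that fits with intention to treat, and whether 6.0 is a raw, change or residual SD. Per named weight contrast at one visit, before covariate adjustment and with BMI outside the family, the figures to give are:
- two-sided: about 83–87% for two contrasts against control, or 79–82% for three pairwise;
- one-sided: about 89–92%, or 86–88%.

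If success is at least one true 4 kg difference, give that power instead, with the assumed pattern of effects. If 6.0 is a raw SD, add the assumed R² and the resulting power.

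The cost is a short text edit, after choices that the Hochberg procedure needs anyway before it can be run. Recruitment ran "for one month from the 25th September to 24th October, 2017", so the number recruited is already fixed; no participants are added, and the Hochberg rule and its error rate stay as they are. The downside is that the stated power may look less favourable.
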